5.3 LIFESTYLE GUIDELINES

5.3.1 CONTRACEPTION

From Screening Visit 1 until their last study visit, all subjects must agree to be strictly abstinent from sexual intercourse or use an acceptable form of contraception as defined by this protocol if the subject or their partner is capable of becoming pregnant.

Acceptable forms of contraception are:

1. Use of a condom for males with a vasectomy (vasectomy must have been performed at least 6 months prior to Screening Visit 1)
2. Males without a vasectomy or a vasectomy performed within 6 months prior to Screening Visit 1 must use a condom and be instructed that their female partner(s), if any, must be

post-menopausal or permanently surgically sterile, or must use another form of birth control which includes the following:

- a. Barrier methods of contraception such as a diaphragms or cervical/vault caps
- b. Established hormonal contraceptive methods. Females who are using hormonal contraceptives must have had consistent use of the same hormonal contraceptive product for at least 4 weeks prior to dosing and must continue to use the same contraceptive during the study
- c. Intrauterine device (IUD)
- d. Tubal ligation/occlusion/division

3. Women who are not post-menopausal or permanently surgically sterile must agree to use birth control (as described in #2 above) and be instructed that their male partner(s) must use a condom

Subjects who withdraw from the study after receiving study medication should remain on an acceptable form of contraception for 24 weeks after their last study injection.

5.4 STRATEGIES FOR RECRUITMENT AND RETENTION

A detailed recruitment and retention plan will be maintained by the Sponsor.

5.5 PARTICIPANT WITHDRAWAL OR TERMINATION

5.5.1 REASONS FOR WITHDRAWAL OR TERMINATION

As the study treatment requires two injections in Phase A and two injections in Phase B, best efforts will be made to encourage subjects to attend all follow-up visits even if they are withdrawn from treatment. Subjects will be informed that they are free to withdraw from the study at any time and for any reason. A premature discontinuation from study will occur when a subject who signed informed consent ceases participation in this study, regardless of circumstances, prior to completion of the defined study period. Subjects can be prematurely discontinued from study medication and/or from the study for one of the following reasons:

- Death
- Lost to follow-up after a minimum of 3 attempts have been made to contact the subject, including sending a registered letter
- Subject withdraws consent
- AE
- Subject non-compliance
- Request by regulatory authority
- Study terminated by Sponsor

The Investigator may withdraw a subject from study medication or the study if, in the Investigator's opinion, it is not in the best interest of the subject to continue with treatment or the study.

5.5.2 HANDLING OF PARTICIPANT WITHDRAWALS OR TERMINATION

In case of premature discontinuation of study participation, ET procedures should be conducted within 14 days of discontinuation for any subject who discontinues after the Day 1 visit, if possible. The date the subject is withdrawn from the study and the reason for the discontinuation should be recorded on the eCRF. The Investigator or designee must complete all applicable eCRF pages for subjects who discontinue from the study prematurely.

Replacement of subjects who withdraw or discontinue prematurely is not allowed.

Subjects who are withdrawn from study medication for safety reasons will continue with all planned study visits per protocol, without any further dosing.

5.6 PREMATURE TERMINATION OR SUSPENSION OF STUDY

The Investigator and the Institutional Review Board/Ethics Committee (IRB/EC) reserve the right to prematurely terminate the study in the interest of subject safety and welfare. The Sponsor reserves the right to prematurely terminate the study at any time for administrative or safety reasons. Written notification, documenting the reason for study suspension or termination, will be provided by the suspending or terminating party to the Investigator, Sponsor, and regulatory authorities as appropriate. If the study is prematurely terminated or suspended, the Investigator will promptly inform the IRB and will provide the reason(s) for the termination or suspension.

6. STUDY AGENT

6.1 STUDY AGENT(S) AND CONTROL DESCRIPTION

6.1.1 ACQUISITION

Samumed will be responsible for the manufacturing, labeling, packaging, distribution, reconciliation, and destruction of study medication product and placebo product related to the study.

6.1.2 FORMULATION, APPEARANCE, PACKAGING, AND LABELING

SM04690 drug substance is an off-white powder. SM04690 drug product is a sterile suspension in diluent containing 0.5% carboxymethylcellulose sodium and 0.05% polysorbate 80 in pH 7.4 phosphate buffered saline. SM04690 drug product is supplied as 2.5 mL of formulated suspension in a ready-to-use 3 mL polypropylene vial. SM04690 placebo product is supplied as 2.5 mL of formulated vehicle in a ready-to-use 3 mL polypropylene vial. SM04690 placebo product contains 0.5% carboxymethylcellulose sodium and 0.05% polysorbate 80 in pH 7.4 phosphate buffered saline.

SM04690 drug product and placebo product are manufactured by Catalent Pharma Solutions, (Woodstock, IL) and will be supplied as a ready-to-use single-use injection. SM04690 drug product and placebo product will be supplied to the study pharmacist and labeled according to the applicable local and country regulations. For dispensing, dose preparation, and labeling instructions, refer to the Pharmacy Manual.

6.1.3 PRODUCT STORAGE AND STABILITY

The study medication and placebo must be stored at the appropriate temperature (15°-30°C or 59°-86°F) and in a restricted area with limited access. Temperature excursions are allowed between 2°-60°C (36°-140°F) for a time period not to exceed a cumulative of 72 hours. Refer to the Pharmacy Manual for detailed instructions on how to manage temperature excursions.

6.1.4 PREPARATION

Each dose of ready-to-use SM04690 drug product or placebo product should be well mixed (the drug product is a suspension) prior to injecting 2 mL intra-articularly into the target knee. Refer to the Pharmacy Manual for detailed instructions on study medication preparation.

6.1.5 DOSING AND ADMINISTRATION

SM04690 will be administered in the following dosage strengths:

- SM04690 0.07 mg in 2 mL Injectable Suspension
- SM04690 0 mg; 2 mL placebo (vehicle) injection only

The injectable investigational product or placebo is to be administered by the Unblinded Investigator as a single injection into the target knee joint once each at Day 1 and Week 24 (Phase A), and once each at Week 52 (EOSa) and Week 76 (Phase B). The Week 24, 52 (EOSa), and 76 injections may occur up to two weeks later than the Week 24, 52 (EOSa), and 76 visits, respectively, to allow for resolution of any intercurrent illness (e.g., infection) prior to the injection. The Unblinded Investigator must minimize any contact with the subject following the injections and may not perform any study assessments throughout the duration of the study. All subject contact for the remainder of the study is limited to the Blinded Investigator and other appropriate blinded study personnel.

Only 1 knee will be treated for each subject in this study. The injections can be done either through lateral or medial (including superior/suprapatellar, midpatellar and inferior/anterior) approaches, based on the standard practice of the Unblinded Investigator or the knee examination of the subject. Although not required, the injections may be guided by ultrasound or fluoroscopy without contrast if it is the standard practice of the Investigator.

Only topical anesthetics are allowed prior to study injection. Any local anesthetic injections are prohibited.

Prior to administration of the intra-articular knee injection, the subject should be blinded to observation of the study medication and injection procedure according to the processes specified in the Site-Specific Blinding Plan.

The Unblinded Investigator (injector) should place the needle into the joint and the total volume contained in the syringe is to be injected into the joint space. Because SM04690 drug product is a suspension, prior aspiration of synovial fluid into the syringe containing the injectate should be avoided to prevent trapping of particles within synovial aspirate/cellular content residues. If it is the standard practice of the injector to aspirate a small amount (0.3-0.5 mL) of joint fluid (if present) to confirm correct needle placement, this will have to be done with a separate empty

sterile syringe and, via syringe exchange, subsequently inject study medication using a new syringe.

6.1.6 ROUTE OF ADMINISTRATION

The injectable investigational product or placebo is to be administered as a single intra-articular injection into the target knee joint once each at Day 1 and Week 24 (Phase A), and once each at Week 52 (EOSa) and Week 76 (Phase B).

6.1.7 STARTING DOSE AND DOSE ESCALATION SCHEDULE

Not applicable to this study. Each subject will be randomly assigned to active or placebo on Day 1.

6.1.8 DOSE ADJUSTMENTS/MODIFICATIONS/DELAYS

No modification in the specified dose concentration or the volume (2 mL) of the study medication or placebo injected into the target knee joint will be allowed.

6.1.9 DURATION OF THERAPY

The injectable investigational product or placebo is to be administered as a single intra-articular injection into the target knee joint once each at Day 1 and Week 24 (Phase A), and once each at Week 52 (EOSa) and Week 76 (Phase B).

At the Week 24, 52 (EOSa), and 76 visits, the Investigator should evaluate the subject for suitability to receive the study medication injection. The subject should not have any condition, including laboratory findings and findings in pre-injection assessments, that, in the opinion of the Investigator, constitutes a risk or contraindication for the injection, or that could interfere with the study objectives, conduct, or evaluation. The injections may occur up to two weeks later than the Week 24, 52 (EOSa), and 76 visits, respectively, to allow for resolution of any intercurrent illness (e.g., infection) prior to the injection. If, in the opinion of the Investigator, the subject should not receive any of the injections, the subject will discontinue treatment but will continue with all planned study visits per protocol.

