5.2 PARTICIPANT EXCLUSION CRITERIA

Any potential subject who meets one or more of the following criteria will not be included in this study:

1. Pregnant and breastfeeding women, and women who are not post-menopausal (defined as 12 months with no menses without an alternative medical cause) or permanently surgically sterile (includes hysterectomy, bilateral salpingectomy, and bilateral oophorectomy) and have a positive or indeterminate pregnancy result at Screening Visit 2 or Day 1
2. Women who are not post-menopausal or permanently surgically sterile, who are sexually active, and who are not willing to use birth control (as outlined in [Section 5.3.1](#)) during the study period
3. Males who are sexually active and have a partner who is capable of becoming pregnant, neither of whom have had surgery to become sterilized or who are not using birth control as outlined in [Section 5.3.1](#)
4. Body mass index (BMI) > 35
5. Partial or complete joint replacement in either knee
6. Currently requires:
 - a. regular use (in the opinion of the Investigator) of ambulatory assistive devices (e.g., wheelchair, parallel bars, walker, canes, or crutches), or
 - b. use of a lower extremity prosthesis, and/or a structural knee brace (i.e., a knee brace that contains hardware)
7. Radiographic disease Stage 0, 1, or 4 in the target knee at Screening Visit 1 according to the Kellgren-Lawrence grading of knee OA as assessed by independent central readers
8. Previous enrollment in a Samumed clinical trial investigating SM04690
9. Any surgery (e.g., arthroscopy) in either knee within 26 weeks prior to Screening Visit 1
10. Any bone fracture(s) within 26 weeks prior to Screening Visit 1
11. Any surgery scheduled during the study period. Non-surgical invasive procedures conducted for a diagnostic or therapeutic purpose scheduled during the study period are not prohibited (refer to [Section 7.6](#)).
12. Significant and clinically evident misalignment of either knee that would impact subject function, as determined by the Investigator
13. History of malignancy within the last 5 years; however, subjects with prior history of in situ basal or squamous cell skin cancer are eligible if completely excised. Subjects with

other malignancies are eligible if they have been continuously disease free for at least 5 years prior to Screening Visit 1

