7.2.2 OTHER ASSAYS OR PROCEDURES

Pregnancy Test

A serum-based pregnancy test will be performed on female subjects at Screening Visit 2 and a urine-based pregnancy test will be performed on female subjects of childbearing potential at Day 1. Results from the pregnancy test will be utilized to determine subject eligibility.

Drug Test

A urine sample for drug testing will be collected at Screening Visit 1. The urine drug test will include: amphetamine, buprenorphine, cocaine, methadone, opiates, phencyclidine (PCP), propoxyphene, barbiturates, benzodiazepine, methaqualone, and tricyclic antidepressants. Results from the drug test will be utilized to determine subject eligibility.

Biomarkers

Blood samples for biomarker analysis will be collected by a qualified staff member at Screening Visit 2 and Weeks 4, 12, 24, 36, 52 (EOSa), 64, 76, 88, and 104 (EOSb) or ET.

Biomarkers that will be assessed in serum include, but are not limited to, bone biomarkers (PINP and β -CTX), and a cartilage biomarker (COMP).

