^b At Day 1, all procedures should be performed prior to study medication injection except for collection of AE and concomitant procedures/medication data.

^c At Week 24, 52 (EOSa), and 76, all procedures should be performed prior to study medication injection.

^d Review medical history to capture End Date(s), if applicable, of any ongoing medical history(ies) collected at screening.

^e Urine pregnancy test on Day 1 will only be performed on female subjects of childbearing potential.

^f Concentrations of bone and cartilage biomarkers are analyzed in the serum.

^g Electronic diary devices will be provided to subjects at Screening Visit 2; subject electronic diary and questionnaire training will be conducted at Screening Visit 2.

^h Electronic diary compliance for daily pain NRS over the screening period will be reviewed at Day 1 prior to randomization to determine subject eligibility.

ⁱ WOMAC questionnaire will be reviewed at Day 1 prior to randomization to determine subject eligibility.

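### No pregnancy test is scheduled before the Week 24, 52 and 76 injections, so no planned procedure would find an unrecognised pregnancy before re-dosing: a minor safety gap, cheap to close

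*Protocol*

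**What the plan says.** Protocol section 7.2.2 schedules two pregnancy tests. The first covers all women: "A serum-based pregnancy test will be performed on female subjects at Screening Visit 2". The second covers those who could become pregnant: "a urine-based pregnancy test will be performed on female subjects of childbearing potential at Day 1". The section gives eligibility as the use of the results. Exclusion criterion 1 (5.2) bars women who are neither post-menopausal nor surgically sterile and who "have a positive or indeterminate pregnancy result at Screening Visit 2 or Day 1".

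The schedule of events (7.3.7) marks each test at one visit only, and footnote e adds: "Urine pregnancy test on Day 1 will only be performed on female subjects of childbearing potential". The procedure lists for Weeks 24, 52 and 76 (7.3.3 to 7.3.5) contain no pregnancy test. Nor does the laboratory panel in 7.2.1, which is stated as a minimum, or its counterpart in SAP 8.2.3.

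Before each repeat injection, 6.1.9 asks the Investigator to judge suitability: "The subject should not have any condition, including laboratory findings and findings in pre-injection assessments, that, in the opinion of the Investigator, constitutes a risk". The same sentence also covers contraindications. The injection can move by up to two weeks "to allow for resolution of any intercurrent illness (e.g., infection) prior to the injection". Section 5.5.1 adds a general power: "The Investigator may withdraw a subject from study medication or the study if" continuing is not in the subject's interest. Section 5.3.1 requires abstinence or contraception through the last visit. Section 8.4.5 has any pregnancy reported and followed to its outcome.

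**The concern.** The protocol holds the first injection to a higher standard than the other three. Screening Visit 2 falls 7 to 16 days before Day 1, and for women of childbearing potential the protocol does not rely on a serum result of that age. It asks for a new test on the day of dosing, and even an indeterminate result bars entry. For the repeat injections, the last scheduled test is months old.

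Exclusion 1 is an entry criterion, and 6.1.9 does not carry it forward. A site that follows the schedule exactly could therefore re-dose a woman whom exclusion 1 would have kept out on Day 1, simply because nobody knew she was pregnant. What is at stake is avoidable exposure of a pregnancy to study drug. The protocol treats such exposure as something to prevent: it tests twice before the first dose and asks subjects who withdraw after dosing to keep using contraception for 24 weeks after their last injection.

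**Working it through.** **Count of scheduled tests, and age of the last result.** The last scheduled test is on Day 1. The latest permitted injection is the nominal visit day plus the visit window plus the 14-day deferral.

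| Injection | New tests scheduled | Nominal days since last test | Latest permitted |
|---|---|---|---|
| Day 1 | 2 | 0 | 0 |
| Week 24 (Day 169, +3) | 0 | 169 − 1 = 168 | 168 + 3 + 14 = 185 |
| Week 52 (Day 365, +7) | 0 | 365 − 1 = 364 | 364 + 7 + 14 = 385 |
| Week 76 (Day 533, +7) | 0 | 533 − 1 = 532 | 532 + 7 + 14 = 553 |

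**Expected number of events.** The plan gives no figure to reproduce. The documents supply three repeat injections and 1:1 allocation. The other inputs are assumptions:

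- women of childbearing potential: 5 to 15;
- pregnancies per 100 woman-years: 0.5 to 2;
- time a pregnancy stays unrecognised: 28 to 56 days;
- early days in which a urine test would still miss it: 14, leaving 14 to 42 detectable days.

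Expected test-detectable pregnancies on SM04690 = women × 3 injections × (detectable days / 365.25) × rate × 1/2.

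- Low: 5 × 3 × (14/365.25) × 0.005 × 1/2 = 0.0014; chance of at least one = 1 − exp(−0.0014) = 0.14%.
- High: 15 × 3 × (42/365.25) × 0.02 × 1/2 = 0.052; chance = 1 − exp(−0.052) = 5.0%.

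This supposes that every such woman receives all three repeat injections. If none entered Phase B, only the Week 24 injection would count, and the range would fall to a third: 0.0005 to 0.017.

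**Can an existing provision find the pregnancy?**

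- Contraception lowers the rate but detects nothing. Women using it are still tested twice before the first injection.
- The suitability check draws on laboratory findings and pre-injection assessments, and no scheduled one tests for pregnancy.
- The minimum wording in 7.2.1 allows an extra test without requiring it.
- Section 8.4.5 acts only once a pregnancy is known.

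None of these is a planned procedure that would find an unrecognised pregnancy.

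**The case against.** The strongest reply is that the exposure is very small and partly covered already. Subjects are aged 40 to 80. Women who can conceive must be abstinent or use a listed method with a partner condom. Each re-dosing visit includes a physical examination and adverse event review, and the Investigator can order a test on suspicion. The dose is 0.07 mg into the joint, and for known risks the protocol (2.3.1) refers to the Investigator Brochure, so whether repeat testing is needed may turn on data outside these documents. Most of this stands, and it limits the weight of the point. It does not supply the missing routine test, because suspicion is what an unrecognised pregnancy lacks.

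Three stronger readings are tempting, and the documents do not support them.

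- A reader might infer that the protocol allows dosing in known pregnancy. No sentence expressly forbids it, but 6.1.9 and 5.5.1 let the Investigator withhold the injection.
- A reader might count every unrecognised pregnancy at dosing in both arms. On the same assumptions that is 5 × 3 × (28/365.25) × 0.005 = 0.006 to 15 × 3 × (56/365.25) × 0.02 = 0.14. It overstates what a test could prevent, because it includes recipients of vehicle, which 2.3.1 describes as inactive substances, and pregnancies too early to detect.
- A reader might want the test read before the scans. The Day 1 standard gives no support: Day 1 has no scans, and Screening Visit 2 sets no order between the serum test and the imaging. Making scans wait for a confirmatory result could push them outside the visit window for no stated benefit.

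**Conclusion.** The gap is real: two tests before injection 1 and none before injections 2, 3 and 4. It is confined to pregnancies nobody has recognised, at three visits. About 0.0014 to 0.052 test-detectable pregnancies would be expected on SM04690 over the trial, but the headcount, pregnancy rate, recognition window and undetectable period are all assumed, and the upper end needs every unfavourable value at once. No size of fetal risk is claimed, because the documents give no systemic exposure or reproductive toxicity data. The case rests on applying the Day 1 standard to each injection at little cost. It is a minor safety improvement.

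**What to change.** In 7.2.2, 7.3.3 to 7.3.5 and 7.3.7, add the Day 1 urine pregnancy test for female subjects of childbearing potential at Weeks 24, 52 and 76. Read it before the injection, and repeat it on the injection day if the injection is deferred. Footnote c of the schedule already says that at these visits "all procedures should be performed prior to study medication injection", so a new row would fall under it. No order relative to the scans is needed.

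In 6.1.9, state that a positive or indeterminate result holds the injection until a confirmatory serum test is back. Use the existing two-week deferral and unscheduled visit, and widen the deferral wording beyond intercurrent illness. If pregnancy is ruled out, the injection proceeds. If it is confirmed, no further injections are given and 8.4.5 follow-up applies. The confirmatory step matters because, under 6.1.9 as written, a decision not to inject ends treatment, so one indeterminate result could do that.

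The cost is up to three urine tests per such woman, at visits where urine is already collected for urinalysis: 5 × 3 = 15 to 15 × 3 = 45 tests under the assumed headcount. If 1% to 3% of results are not clearly negative (assumed), that means 15 × 0.01 = 0.15 to 45 × 0.03 = 1.35 serum tests in the whole trial, each with a possible short injection delay.

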6.1.10 TRACKING OF DOSE

Not applicable to this study.

6.1.11 DEVICE SPECIFIC CONSIDERATIONS

Not applicable to this study.

6.2 STUDY AGENT ACCOUNTABILITY PROCEDURES

All used and unused study medication and placebo vials received must be returned and accounted for. All injections prepared and dispensed must also be logged. The log includes the following:

- Subject number and initials
- Date that study medication was injected
- Quantity dispensed (active vial, placebo vial)
- Quantity returned/used (active vial, placebo vial)

All study medication and vehicle dispensed by the Unblinded Investigator and/or unblinded designee will be inventoried and accounted for throughout the study. The Unblinded Investigator and/or unblinded designee must maintain an accurate, up-to-date dispensing log for all study medications supplied by the Sponsor. Study medication and placebo dispensed for all subjects must be recorded on the drug accountability forms. The study medication dispensing log and remaining drug inventory will be reviewed by the Sponsor-designated unblinded clinical monitor.

The study medications supplied for this study are for use only in subjects properly consented and randomized into this protocol. Used and unused study medications must be kept in a secure, blinded location physically separated from standard clinic or office drug supplies, and with access limited to the Unblinded Investigator and/or unblinded designee. Procedures for Unblinded Investigator return or destruction of used and unused vials of the study medication and placebo will be provided in the Pharmacy Manual.

